#### **3.4.2.6 Other Endpoints**

##### Time to Response

Time to response (TTR) is defined as the time from randomization until the first documentation of a subsequently confirmed OR. Only subjects who have achieved OR (confirmed CR or confirmed PR) will be evaluated for TTR. TTR is defined in months as follows:

TTR (months) = (Date of first confirmed disease response – Date of randomization + 1) / (365.25/12).

The median TTR and its 95% CI will be assessed using the Kaplan-Meier method. The number of subjects with response at different disease assessment timepoints may be provided.

##### Change from Baseline in Tumor Sizes

The percent change from baseline in target lesion sum of diameters (longest for non-nodal lesions, short axis for nodal lesions) will be calculated at each evaluable post-baseline disease assessment (DA) # X (X = 1, 2, 3, etc.). The percent change from baseline in target lesion sum of diameters is defined as follows:

$$\%Chg\ at\ DA\ #X = 100 \times \frac{\sum\ Diameters\ at\ DA\ #X - \sum\ Diameters\ at\ DA\ at\ baseline}{\sum\ Diameters\ at\ DA\ at\ baseline}$$

The percent change from baseline in target lesion sum of diameters will be presented by subject using spider plots. The best percent change from baseline in target lesion sum of diameters is defined as the largest reduction or smallest increase (in the case where a reduction does not occur) from baseline observed over all post-baseline disease assessments until disease progression. The best percent change from baseline will be presented using waterfall plots. Target lesion measurements and sum of diameters will be listed by disease assessment and subject.

### **3.4.3 Handling of Dropouts and Missing Data**

In general, missing data are not imputed for statistical analysis. Guidance regarding the handling of dropouts, missing data, and censoring will apply uniformly to all efficacy analyses resulting from an application of RECIST v1.1 to investigator assessed tumor measurements. For investigator reported outcomes, analyses will present outcomes without consideration of missing data or censoring rules.

### **3.4.4 Subgroup Analyses**

To assess the consistency of treatment effects, the analyses of ORR and PFS will be performed by the following subgroups:

- Age (< 70,  $\geq$  70 years)
- Sex (Female, Male)
- Race (Asian, non-Asian)
- Histology (Squamous, non-Squamous)
- Smoking status (Smoker, never smoker)
- ECOG performance status at baseline (0, 1)
- PD-L1 status (Positive, Low/Negative, Unknown) based on 1% and 25% cuts separately
- Platinum agent (Cisplatin, Carboplatin)
- Time from last radiation to randomization (<14 days,  $\geq$ 14 days)
- Disease stage at study entry (IIIA, IIIB/C)

Forest plots will be provided for difference in ORR (confirmed/unconfirmed response and confirmed response, separately) and PFS hazard ratios.

### **3.4.5 Other Efficacy Analyses**

Confirmed/unconfirmed ORR will be reported along with the primary analysis of confirmed ORR. Analyses will be conducted in the same way as described in Section 3.4.1.

Similarly, confirmed/unconfirmed DCR, DoR and TTR will be reported, with analyses conducted in the same way as described in Section 3.4.2.

The proportion of subjects progression-free and alive at 6 months (PFS-6) and 9 months (PFS-9) and the associated 95% CIs may be estimated using the Kaplan-Meier method.

CCI

The number and percentage of subjects with distal metastasis at 6 months based on PET scan may be reported.

### **3.5 Pharmacodynamic Endpoint(s) and Analyses**

Exploratory analysis of pharmacodynamic endpoints may be described separately.

## **3.6 Safety Analyses**

All safety analyses will be performed based on the As-treated population, unless otherwise specified. Only post-baseline visits up to and including 90 days following the date of last dose of study medication will be considered in derivations.

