#### **4.8.7 Interim Analysis**

Interim analyses will be conducted during the course of the study to evaluate the clinical activity and safety of any experimental arm in comparison with the control arm. The results of the interim analyses may be used for internal program decision and/or potential interactions with regulatory agencies on future development. The first interim analysis will be performed once the control arm has 30 ITT subjects who have reached the data cutoff criteria (defined as the opportunity to be followed for at least 16 weeks at the time of data cutoff). The DCR at Week 16 will be used for No-Go decision, and ORR may be used for early Go decision. Enrollment will not be paused for interim analyses.

Bayesian PP will be used to evaluate clinical activity ([Lee and Liu, 2008](#)). [Table 10](#) illustrates the sample algorithm to make a No-Go decision based on DCR at 16 weeks at the interim analysis when the control arm and an experimental arm each have 30 subjects. If an early No-Go decision is made, enrollment to the corresponding experimental arm will be stopped. In

this study, we assume a target value (TV) of  $\Delta$ DCR at 16 weeks as 15%, where  $\Delta$ DCR is the difference in DCR between an experimental arm and control arm.

- An experimental arm will meet the No-Go criteria if the probability that the true  $\Delta$ DCR is larger than TV is less than 10%, ie,  $\text{Prob.}(\text{True } \Delta\text{DCR} > 0.15) < 0.10$ . A No-Go decision will be made at an interim analysis if the PP of meeting the No-Go criteria given observed data is greater than 95%, ie,  $\text{PP}[\text{Prob.}(\Delta\text{DCR} > 0.15) < 0.10] > 0.95$ .

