### **2.4 Sample Size**

Sixty subjects will be enrolled in each of the combination therapy experimental arms and more than 60 subjects will be enrolled in the durvalumab control arm dependent upon the length of the study. The sample size of 60 subjects per experimental arm is not designed to make explicit power and Type I error considerations for a hypothesis test. It is primarily chosen to obtain a preliminary assessment of antitumor activity with a certain degree of precision.

Table 2.4-1 shows estimated differences in objective response rate (ORR) between an experimental arm and control arm along with 2-sided 95% exact CIs with a sample size of 60 subjects each. Sixty subjects per treatment arm provides a 95% CI with reasonable width (approximately  $\pm 18\%$ ) for the estimated ORR difference between a durvalumab combination experimental arm and the durvalumab control arm. For a 20% increase in ORR in any durvalumab combination experimental arm over durvalumab control arm (50% vs 30%, respectively), the lower limit of the 95% CI for the difference between these arms is 1%, which is greater than 0%, suggesting that the durvalumab combination experimental arm will have a higher ORR than the durvalumab control arm with 95% confidence.

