### 3 STATISTICAL METHODS

#### 3.1 General Considerations

Tabular summaries will be presented by treatment group. Categorical data will be summarized by frequency distribution (number and percentage of subjects falling within each category). Continuous variables will be summarized by descriptive statistics including N, mean, standard deviation, median, and range (minimum and maximum). All available data will be used, and thus missing data will not be imputed, unless otherwise specified. In general, subjects with missing data for a parameter will be excluded from the summary of this parameter. Tables will be supported by data listings showing the original data forming the basis for the summaries. Data listings will be sorted by treatment group, subject number and date collected where applicable.

Unless stated otherwise, two-sided confidence intervals will be produced at 95%. Baseline values will be defined as the last valid assessment prior to the first administration of IP. Assessments on the day of the first dose where neither time nor a nominal pre-dose indicator are captured are considered prior to the first dose if such procedures are required by the protocol to be conducted before the first dose.

Data analyses will be conducted using the SAS® System (SAS Institute, Inc., Cary, NC, USA) Version 9.4 or above, unless otherwise specified. All analysis outputs will be validated according to MedImmune SAS programming standards and MedImmune validation procedures.

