**Table 3.2-1      Analysis Populations**

Population	Description
Intent-to-treat (ITT) Population	The ITT population includes subjects who are randomized. Subjects will be analyzed according to their randomized treatment group.
As-treated Population	The As-treated population includes all subjects who receive any IP. Subjects will be analyzed according to the treatment they really receive.
Response-evaluable Population	The Response-evaluable population includes subjects from the As-treated population who have a baseline disease assessment (DA), have the opportunity to be followed for at least 16 weeks at the time of the DCO (i.e., dosed at least 16 weeks prior to the time of the DCO), and either has at least one post-baseline disease assessment and/or discontinued treatment due to death or disease progression. The response-evaluable population will not be used for the final analysis.

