## **3.4 Efficacy Analyses**

### **3.4.1 Primary Efficacy Endpoint(s) and Analyses**

#### **3.4.1.1 Primary Efficacy Endpoint(s) and Analysis**

The primary efficacy endpoint is objective response (OR) per Response Evaluation Criteria in Solid Tumors version 1.1 (RECIST v1.1). ORR is defined as the proportion of subjects with a best overall response of confirmed CR or confirmed PR that occur prior to disease progression, and/or prior to the initiation of subsequent anticancer treatment. Confirmation of response requirements are defined in [Section 3.4.2.1](#) for best overall response. The primary analysis of ORR will be based on the ITT population. An estimate of the difference in ORR as well as its 2-sided 95% exact CI between each experimental arm and control arm will be reported. The rates between each experimental arm and control arm will be tested for significance with a Cochran–Mantel–Haenszel test, stratified by histology (adenocarcinoma or non-adenocarcinoma). Subjects that have missing overall response assessments will be considered as non-responders, and will therefore be counted in the denominator, but not in the numerator of ORR. Primary efficacy analysis will include control subjects that are concurrently enrolled with each experimental arm.

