### **3.4.2 Secondary Efficacy Endpoint(s) and Analyses**

The secondary efficacy endpoints include disease control (DC); duration of response (DoR); progression-free survival (PFS); progression-free survival at 12 months (PFS-12) and overall survival (OS). The efficacy endpoints will be summarized based on the ITT population and may be based on the Response-evaluable population as a supportive analysis. For analyses that involve an arm comparison between an experimental arm and control arm, only control subjects that are concurrently enrolled with the experimental arm will be included.

Efficacy analyses, except for OS, will be based on an application of Response Evaluation Criteria in Solid Tumors (RECIST) 1.1 ([Eisenhauer et al, 2009](#)) to investigator assessed tumor measurements.

Programmatic derivation guidance used for the application of RECIST v1.1 is provided in [Appendix 7.1](#). RECIST v1.1 guidelines will be used to determine disease response.

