## 4 INTERIM ANALYSIS

Interim analyses comparing durvalumab in combination with novel agents to durvalumab alone will be performed in a continuous manner using a joint Bayesian predictive probability. Bayesian predictive probability has been used in the setting of single-arm trials with tumor response endpoints such as OR and allows for continuous assessments for early Go/No-Go decision making ([Lee and Liu, 2008](#)). A joint Bayesian predictive probability approach

allows for continuous assessments of the delta ( $\Delta$ ), or difference, of the DCRs between durvalumab/novel agent combinations and durvalumab alone ([Pulkstenis et al., 2017](#)).

Interim analyses will begin after approximately 30 subjects in control arm (durvalumab alone) have been randomized and have reached the data cutoff criterion. The data cutoff criterion is defined as the opportunity to be followed for at least 16 weeks at the time of the data cutoff (i.e., dosed at least 16 weeks prior to the time of the data cutoff). The interim analysis will be based on the subset of the ITT Population that have satisfied the data cutoff criteria. Enrollment will not pause during the interim analysis before the decision is made.

Following this initial interim analysis, subsequent interim analyses will be performed for each experimental arm regardless of whether it starts enrollment later than control arm. Specifically, an interim analysis will be performed once each experimental arm has approximately 30 ITT subjects reach the data cutoff criterion. For interim analyses that will lead to an early No-Go decision, a response is defined as either a confirmed or unconfirmed CR or PR as per RECIST v1.1. Only concurrent control subjects, i.e., enrolled during the same period as the experimental arm, will be included in interim analyses. A comparison of each experimental arm versus all control subjects may be included as a supportive analysis.

The Target Value (TV) is set to demonstrate a 15% increase in  $\Delta$ DCR at 16 weeks, where  $\Delta$ DCR is the difference in DCR between an experimental arm and control arm. At final analysis, No-Go criteria will be met if the probability that the true  $\Delta$ DCR exceeds the prespecified TV of 15% is less than 10% (i.e., No-Go:  $P[\Delta\text{DCR} > \text{TV}] < 10\%$ ).

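### The descriptive safety tables have no concurrent-control restriction, although efficacy arm comparisons and interim analyses do, so an arm's adverse events may be read beside a different control group

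*SAP*

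**What the plan says.** **Efficacy comparisons.** SAP 3.4.1.1: "Primary efficacy analysis will include control subjects that are concurrently enrolled with each experimental arm". SAP 3.4.2 extends this to secondary endpoints wherever two arms are compared: "only control subjects that are concurrently enrolled with the experimental arm will be included". A comparison with all controls is only an optional sensitivity analysis (SAP 3.4.1.2).

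**Interim analyses.** SAP 4: "Only concurrent control subjects, i.e., enrolled during the same period as the experimental arm, will be included in interim analyses". The all-controls version is again optional and supportive.

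**Safety.** SAP 3.6: "All safety analyses will be performed based on the As-treated population, unless otherwise specified". Table 3.2-1 defines the population without reference to period: "The As-treated population includes all subjects who receive any IP". SAP 3.1 sets the display: "Tabular summaries will be presented by treatment group". Nothing in SAP 3.6.1 to 3.6.6 narrows the control group by enrolment period. The SAP version history records the version 2.0 clarification on concurrent controls for efficacy analyses only.

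**Baseline.** SAP 3.3.2 summarises the whole ITT population by treatment group, also without a concurrency limit.

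**Control numbers.** SAP 2.4 foresees that "more than 60 subjects will be enrolled in the durvalumab control arm dependent upon the length of the study". Protocol 4.1.1 is more cautious: the total might exceed 60 because new arms may be added.

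**The concern.** Concurrent controls are used in a platform trial because subjects randomised over the same period share eligibility rules, case mix and background care. That reasoning applies to adverse-event rates as much as to response. Controls from outside an arm's enrolment period bring a non-randomised element into whatever is read from the columns.

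Safety of durvalumab alone and in combination is a secondary objective. Readers will set the combination column beside the control column to judge added toxicity, and will set that against the response and progression-free survival results. If the two control groups differ, the benefit reading and the harm reading for the same arm have different reference groups, and the tables would not show it.

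**Working it through.** **1. The plan's own figures.** No figure in either document bears directly on this point. The only precision basis is the ORR table (Protocol Table 9, SAP Table 2.4-1). Its four intervals reproduce with an exact unconditional interval on the raw difference (Santner-Snell). For 30/60 versus 18/60, a 0.25-point grid gives 1.5% to 37.5%, against the stated 1% to 38%; the true limits lie up to one grid step outside. The point does not depend on this table.

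**2. Can the control groups differ under the plan?**
- Arms may open sequentially or in parallel (Protocol, Figure 1 notes).
- No subject entered Arm B before Amendment 2 (Protocol 9.3). This does not say that any control had been enrolled by then.
- If no experimental arm is open, a subject already in screening when the arm closed for safety may still enter, but only into control (Protocol 4.6.1, SAP 2.3). Such a control is not randomised against that arm.
- Amendment 3 widened the window from chemoradiotherapy to randomisation from 28 to 42 days and added an exclusion (Protocol 9.2), so eligibility changed over time.

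So they can differ. Whether they did, and by how much, is not stated.

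One detail needs settling. Protocol 4.1.4 counts a subject as enrolled from consent. On a consent date, a subject screened before a safety closure would count as concurrent; on an allocation date, not. The SAP does not say which date defines concurrency. The statement that these subjects fall outside the efficacy comparison uses the allocation date.

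**3. Size.** Let *p* be the event rate in concurrent controls, *d* the difference in rate for non-concurrent controls, and *f* their share of all treated controls.

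Pooled control rate = (1 − *f*)·*p* + *f*·(*p* + *d*) = *p* + *f*·*d*

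The control column moves by *f*·*d*, and the apparent excess of the experimental arm moves by the same amount in the opposite direction. With 60 concurrent and *n* non-concurrent controls, *f* = *n*/(60 + *n*). Both *n* and *d* are assumptions.

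| *n* | *f* | *d* = 5 points | *d* = 10 points | *d* = 15 points |
|---|---|---|---|---|
| 0 | 0% | 0 | 0 | 0 |
| 10 | 14% | 0.7 | 1.4 | 2.1 |
| 20 | 25% | 1.3 | 2.5 | 3.8 |
| 30 | 33% | 1.7 | 3.3 | 5.0 |
| 60 | 50% | 2.5 | 5.0 | 7.5 |

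**4. Scale.** Protocol 1.4.1 gives a Grade 3 or 4 rate of 142/475 = 29.9% on durvalumab in the earlier Phase 3 study. At 30% with 60 versus 60, the standard error of a difference is √(2 × 0.3 × 0.7 / 60) = 8.4 points. Every value in the table is below one standard error. Unlike sampling error, however, the shift does not shrink as controls accumulate at a fixed share.

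**The case against.** The strongest reply is that concurrency follows comparison, not benefit versus harm. SAP 3.4.2 applies it to analyses that compare arms. Safety is to be evaluated, not compared: SAP 3.6 plans counts, percentages, descriptive statistics and shift tables, with no difference, interval or test. This stands. A reader might infer that the plan biases a formal harm comparison, or that all efficacy output uses concurrent controls only. The documents support neither: no safety difference is estimated, and the rule does not reach single-arm efficacy summaries.

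A reader might also infer that interim and final safety are set to use different control groups. Protocol 4.8.7 does say interim analyses are "to evaluate the clinical activity and safety of any experimental arm in comparison with the control arm", and SAP 4 admits only concurrent controls. But SAP 4 describes decisions on disease control and never mentions safety tables, so the mismatch is an inference from joining two documents.

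Evidence that non-concurrent controls exist is thin. Only Arms A and B are described, and by Amendment 4 all subjects had completed their treatment period (Protocol 9.1). If the two arms largely overlapped, the control groups nearly coincide. The 60-extra row implies 120 controls, close to fully sequential arms, which nothing in the documents shows. The statistical programming plan, not provided, holds the table templates and could add a restriction.

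Pooling also has a use: at a 29.9% rate, going from 60 to 120 controls narrows the 95% half-width of a difference from 16.4 to 14.2 points. Some drift would be visible, since SAP 3.3.2 tabulates time from last radiation and SAP 3.6.1 allows stratified adverse-event results.

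These replies limit the weight of the point. They do not remove the gap: the SAP does not say whether the safety control column matches the efficacy control group, and descriptive tables still inform benefit-risk conclusions.

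**Conclusion.** The point holds as an inconsistency in which controls are used, and correcting it is a cheap improvement. As written, the safety control column takes in all treated controls, while efficacy arm comparisons take in only concurrent ones. That the column pools everyone follows from the population definition and the absence of any restriction; no sentence says so outright.

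The effect on the side-by-side reading is *f*·*d*: 0.7 to 7.5 points over the assumed grid, in either direction, and zero if the groups coincide. That range is illustrative and not an estimate of bias in this trial. Nor do the documents support saying that benefit and risk cannot be read together; they can wherever the two control groups are the same.

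**What to change.** In SAP 3.6:

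1. State how many As-treated controls are non-concurrent with each experimental arm, using the concurrency flag that efficacy already needs. State the date that defines it; allocation date would separate out controls entered after a safety closure.
2. If the number is zero, say so, and nothing further is needed.
3. If it is not zero, show the key AE, SAE and AESI summaries, and the SAP 3.3.2 baseline summary, for that arm beside its concurrently enrolled controls.
4. Keep the all-controls column.
5. Base any stated excess over control on the concurrent column.

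The cost is a few sentences, a few extra table columns, and slightly fewer controls in the comparison column. No new data are needed.

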### **3.6.1 Adverse Events and Serious Adverse Events**

Adverse events will be coded by Medical Dictionary for Regulatory Activities (MedDRA) version 26.0 and the type, incidence, CTCAE grade and relationship to study IP will be summarized. Specific adverse events will be counted once for each subject for calculating percentages. In addition, if the same adverse event occurs multiple times within a particular subject, the maximum CTCAE grade and level of relationship observed will be reported. If any associations of interest between adverse events and baseline characteristics are observed, additional stratified results may be presented.

Treatment-emergent adverse events (TEAEs) are defined as events present at baseline that worsen in intensity after administration of study IP or events absent at baseline that emerge after administration of study IP. All TEAEs that occurred on and after first dose up to 90 days after last dose of IP (any) will be summarized overall, as well as categorized by MedDRA System Organ Class and Preferred Term. In addition, all TEAEs with an onset date no more than 90 days after the last dose of IP (any) will be listed.

The AEs occurring from the signing of the informed consent and prior to the initiation of study IP will be listed.

